3.5.2 Regulatory approval

The Atalante system including its parts and accessories is considered as a Class IIa medical device following Rule 9, according to the annex VIII, according to the regulation (EU) 2017/745 and is covered by a EU certificate N° MDR 727 876 R000 issued by BSI on May 26th, 2021.

3.6 Intervention

The intervention will be delivered through the Neurorehabilitation Cemcat team.

Traditional Gait Rehabilitation training (tRHB):

Participants randomize to receive a tRHB, will be trained 3 times per week, with an intensity of 40 to 60 minutes, and duration over 8-weeks. Progression will occur by increasing the session intensity weekly.

A standardized protocol based on the usual clinical practice of physiotherapy in people with multiple sclerosis will be follow, according to patient characteristics, to design the sessions based on the patient objectives to be achieved, choosing the type of specific exercises to be performed based on the patient's condition and with the possibility of adapting them to their evolution during the twenty-four sessions.

PHYSIOTHERAPY TREATMENT PROTOCOL			
Goal	To re-educate the balance (sitting and standing).	To normalize upper limbs muscle tone	To improve the upper limbs muscular balance (MB)
Intervention	Trunk work on stable surface: anterior-flexion, lateralization and turns to make appear the straightening reactions (5 minutes)	Local cryotherapy application to the most affected muscles using cold-packs (15 minutes)	If BM = 1: isometrical exercises of deltoid, bicep, triceps, carpal extensors and carpal flexors (3 sets of 5 repetitions for each muscular group)
	Trunk work on instable surface (air cushion): anterior flexion, lateralization and turns to make appear the straightening reactions (5 minutes)	Inhibitory postural treatment in flexion, abduction and external rotation of humeral-scapula for the flexor patterns during cryotherapy application	If MB = 2: Weight-bearing and/or active-assisted exercises for deltoids, biceps, triceps, carpal extensors and carpal flexors (3 sets of 5 repetitions for each muscle group)
	Balance work with Bobath ball (5 minutes)	Passive mobilizations and myotendinous stretching of spastic musculature (5 minutes)	If MB= 3 : active-resisted exercises with $\frac{1}{2}$ kg of deltoid, bicep, triceps, carpal extensors and carpal flexors (3 sets of 5 repetitions for each muscular group)
	Balance standing exercises at bars: antero-posterior and lateral load transfer, different support bases, and changing props and surfaces (10 minutes)	Pectoral and brachial biceps kneading and lats stretching (5 minutes)	If MB = 4: active-resisted exercises with 1 kg of deltoid, bicep, triceps, carpal extensors and carpal flexors (3 sets of 5 repetitions for each muscular group)

	Sitting		If MB = 5: active-resisted exercises with 2 kg of deltoid, bicep, triceps, carpal extensors and carpal flexors (3 sets of 5 repetitions for each muscular group)
	If Motor Assessment Scale score (MAS) \leq 4: sitting program low level		Proprioceptive neuromuscular facilitation exercises (Kabat): diagonal on flexion-adduction-external rotation with shoulder pivot; diagonal on flexion-adduction-external rotation with elbow pivot (3 sets of 5 repetitions for each muscular group)
	If Motor Assessment Scale score (MAS) $>$ 4: sitting program medium-high level		
	Standing		
	If Berg scale score \leq 32: standing program low level		
	If Berg scale score 33-43: standing program medium level		
	If Berg scale score \geq 44: standing program high level		
Goal 1	To re-educate the gait	To normalize lower limbs muscle tone	To improve the lower limbs muscular balance (MB)
Intervention	Spastic gait re-education exercises with emphasis on triple flexion during swing phase and initial heel strike to prevent foot drag (5 minutes)	Local cryotherapy application to the most affected muscles using cold-packs (15 minutes)	If BM = 1: isometrical exercises of major glutes, psoas, quadriceps, hamstrings and anterior tibial (3 sets of 5 repetitions for each muscular group)
	Walking on parallel bars with obstacles with emphasis on the triple flexion, on the dissociation of the shoulder and pelvic girdles and on the locking and unlocking of the knees (5 minutes)	Inhibitory postural treatment in abduction, external rotation and triple flexion for the extensor patterns during cryotherapy application	If MB = 2: discounted exercises and/or active-assisted of major glutes, psoas, quadriceps, hamstrings and anterior tibial (3 sets of 5 repetitions for each muscular group)
	Ataxic gait exercises (5 minutes)	Passive mobilizations and myotendinous stretching of spastic musculature (5 minutes)	If MB = 3: active-resisted exercises with $\frac{1}{2}$ kg of major glutes, psoas, quadriceps, hamstrings and anterior tibial (3 sets of 5 repetitions for each muscular group)
	Incorporation of the most appropriate technical aid if necessary	Gastrocnemius kneading and adductors, hamstrings, sural triceps, quadriceps and psoas stretching (5-10 minutes for each limb)	If MB = 4: active-resisted exercises with 1 kg of major glutes, psoas, quadriceps, hamstrings and anterior tibial (3 sets of 5 repetitions for each muscular group)

	Running treadmill with speed and inclination according to tolerance (2-6 minutes)	Passive verticalization at standing or inclined plain to reduce the flexor musculature hypertonia (10 minutes)	If MB = 5: active-resisted exercises with 2 kg of major glutes, psoas, quadriceps, hamstrings and anterior tibial (3 sets of 5 repetitions for each muscular group)
	Weight-bearing walking (5 minutes).	Active verticalization at the shoulders or parallel bars in order to reduce the hypertonia of the flexor muscle (5-10 minutes)	Step from sitting to standing (3 sets of 5 repetitions)
	Vibratory stimulation in bilateral plantar zone (5 minutes)	Antero-posterior and lateral pelvic tilting exercises to encourage straightening reactions and reduce upper limbs hypertonia. (5-10 minutes)	Go up and down 20 stair's steps
		Pelvic and trunk rotations to decrease trunk extension hypertonia (5 minutes)	Active-resisted cycloergotherapy, resistance according to symmetry (10 minutes)
		Passive cycle ergotherapy adapting speed to tolerance and avoiding spasms during exercises (10 minutes).	

Atalante Gait training (RAGT):

Participants randomize to receive a Atalante gait training, will be trained 3-times per week, with an intensity of 40 to 60 minutes, and duration over 8-weeks. Progression will occur by increasing the session intensity weekly. Training intensity will be monitored and standardized using the Borg Rating of Perceived Exertion scale, and will progress from 'fairly light' to 'somewhat hard'. This prescription is consistent and appropriate for individuals with MS with mobility impairment and low fitness levels. Progression will occur by increasing the intensity of the session increase the number of steps in each session and decrease the level of assistance. Sessions will not exceed 60 minutes. We will record all training parameters.

Using the Atalante System, participants will be secured with the appropriately sized harness and attached to an overhead body-weight support system. Each session will begin with a 3–5-minute warm-up in the continuous passive mode (cadence ~40-45 steps/minute). The participant will then be transitioned into the adaptive training phase for practicing repetitive floor walking for up to 30 minutes. During this phase, the force produced by the robot is modulated to support the effort of the patient in producing a typical walking pattern.

Goals	Session n°/time	1 session. "Take in contact"/40 min	2nd and 3rd session / 30 min	2nd week / 30 - 35 min	3rd week / 35-40 min approx)
Improve the muscular balance of the deficient muscles of the lower limbs.	Robotmins assistance level (adapted to the patientmin's capacity)	100%	95%	90%	85%
Reeducate the balance in standing.		Take patient measurements and create the APP's profile	the accelerometer training	Walking with earlygait 5 for 10 min	Walking with earlygait mode 5min
Achieve a stable active bipedestation .		Learn how to change position from sitting (ST) to standing (SD) and back to ST.	Squat exercise 1 series x 5 rep.	Squat exercise 1 series x 10 rep.	The exoskeletonmin's controller is introduced to the patient in earlygait mode 5min.
Improve walking speed and gait pattern.		Learn how the accelerometer works from SD.	Trunk control exercises with balloon for 5 min	Trunk control exercises with ball 5min	Squat exercise 1 series x 10 rep.
Improve stability and safety while driving.		Learn how the movements and weight transfer work to activate the different functions/exercises .	Introduce the realgait mode walking (100% assisted)	Squat exercise 1 series x 5 rep.	Trunk control exercises with ball for 5 min.
Increase resistance to fatigue during walking.		Start by walking for 5 min with early-gait mode. Learn the turns, lateral steps, and "reverse march."	Walking with earlygait 5 for 5 min	Trunk control exercises with balloon for 5 min.	Squat exercise 1 series x 10 rep.
Activities		Start trunk control exercises with a ball for 5 min, and learn how to squat and lateral transfers.		Realgait mode walk for 5 min (100% assisted)	Trunk control exercises with balloon 5min.
		A series of squats x 5 reps.		Realgait walk for 5 min. (Introduce assistance levels, 95% if the patient tolerates)	March with earlygait mode 5min dual task.
		Trunk control exercises with balloon 5min.			Realgait mode for 10 min (adjust levels of assistance based on tolerance)

					and/or patient characteristics).
Session n°/time	4th week / 40 min	5th week / 40 min	6th week / 40 min	7th week / 40 min	8th week / 40 min
Robotmins assistance level (adapted to the patientmins capacity)	80%	75%	70%	65%	60%
	Walking in earlygait mode for 5 min	Walking in earlygait mode for 10 min directed by patient	Walking in earlygait mode for 5 min directed by the patient	Walking in earlygait mode for 5 min directed by the patient	Walking in earlygait mode for 5 min directed by the patient
	Walking in earlygait mode for 5 min directed by the patient	Squat exercise 1 series x 10 rep.	Squat exercise 1 series x 10 rep.	Squat exercise 1 series x 10 rep.	Squat exercise 1 series x 10 rep.
	Squat exercise 1 series x 10 rep.	Trunk control exercises with ball for 5 min.	Trunk control exercises with ball for 5 min.	Trunk control exercises with ball for 5 min	Trunk control exercises with ball for 5 min.
	Trunk control exercises with ball for 5 min.	Squat exercise 1 series x 10 rep.	Squat exercise 1 series x 10 rep.	Squat exercise 1 series x 10 rep.	Squat exercise 1 series x 10 rep.
	Squat exercise 1 series x 10 rep.	Trunk control exercises with balloon 5min.	Trunk control exercises with balloon 5min.	Trunk control exercises with balloon for 5 min	Trunk control exercises with balloon for 5 min
	Trunk control exercises with balloon for 5 min.	Squat exercise 1 series x 5 rep.	Squat exercise 1 series x 10 rep.	Squat exercise 1 series x 10 rep.	Squat exercise 1 series x 10 rep.
	Walking in earlygait mode for 5 min + dual task.	Walking with earlygait 5min dual task.	Trunk control exercises with racket/basketbal l for 5 min.	Trunk control exercises with racket/basketbal l for 5 min.	Trunk control exercises with racket/basketbal l for 5 min
Activities	Walking in earlygait mode for 10 min (We adjust assistance levels)	Walking in earlygait mode for 5 min (We adjust assistance levels)	Walking in realgait mode for 5 min, introducing dual task.	Walking in realgait mode for 10 min directed by the patient (We adjust assistance levels).	Walking in realgait mode for 10 min directed by the patient (We adjust assistance levels).

	Introduce use of the controller by the patient in realgait 5min.	Walking in realgait mode for 10 min directed by the patient (We adjust assistance levels).	Walking in realgait mode for 5 min, training dual task.	Walking in realgait mode for 5 min, training dual task.
--	--	--	---	---

4 Statistical considerations

The sample size calculation was based on the observed success rate (70%) in a previous evaluation of safety and performance of the self-balancing walking system Atalante in patients with spinal cord injury (i.e., 10 mWT with continuous walking mode)¹⁵

A sample size of 15 patients had been deemed necessary to demonstrate the performance with an alpha risk of 5% and a statistical power of 80% (Two-sided test).

Descriptive statistics (i.e., mean, standard deviation) will be calculated for quantitative data (demographics and clinical characteristics and outcome measures). Frequencies will be calculated for qualitative variables. For the proportions, binomial proportion confidences will be calculated using the Wilson formulae. Proportions will be compared using the Newcombe formulae

The Wilcoxon bilateral matched-pairs test will be used to compare repeated measurement on a single sample (mean, standard deviation).

Study data were collected and managed using REDCap electronic data capture tools hosted at the Mayo Clinic. REDCap (Research Electronic Data Capture) is a secure, web-based application designed to data capture for research studies, providing: 1) an intuitive interface for validated data entry; 2) audit trails for tracking data manipulation and export procedures; 3) automated export procedures for seamless data downloads to common statistical packages; and 4) procedures for importing data from external sources (Harris et al., 2009).

5 References

6. Larocca NG. Impact of Walking Impairment in Multiple Sclerosis Perspectives of Patients and Care Partners Conclusions: Difficulty walking is a common impairment in people with MS, with adverse effects on the QOL of people with MS and care partners of a person with MS. *Patient.* 2011;4(3):189-201.

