comes in a clinically meaningful way in PwMS, RAGT seems more effective compared to conventional rehabilitation, while it shows similar effects if compared to specific balance and gait training in studies with level 2 evidence.¹¹ RAGT has several advantages in terms of patient motor assistance, intensity of training, safety, and the possibility to combine other therapeutic approaches and should be promoted for PwMS with severe disability in a multimodal rehabilitation context as an opportunity to maximize recovery.¹¹ In this context is needed a further larger-scale, better-designed RCTs with a longer training duration and more studies evaluating the satisfaction, usability and effectivity of RAGT.^{10 12 13 11}

The Atalante exoskeleton is composed of an external, powered, motorized orthosis that is placed over a person's limbs to provide self-ambulation functions without the use of crutches or other technical aids. The main feature of the exoskeleton is that it is fully actuated with 12 actuated degrees of freedom: three at each hip, one at each knee, and two at each ankle.^{14 15}

The molecular bases associated with the functional improvements derived from rehabilitation therapies or physical exercise are not yet well defined. However, both rehabilitation and exercise have been recognized for their immunomodulatory properties. In fact, recent clinical and preclinical findings have established a connection between physical activity and rehabilitative interventions with discernible epigenetic alterations in immune cells. For example, recent preclinical research has demonstrated how moderate-intensity training induces lasting changes in chromatin accessibility in macrophages, resulting in moderation of their inflammatory responses. However, there is still a lack of comprehensive epigenomic studies examining the repercussions of rehabilitation therapies in individuals with multiple sclerosis.

2 Aims

2.1 Primary Aim:

- To compare the effect of RAGT by use of Atalante self-balance exoskeleton with conventional rehabilitation training (cRHB) for improving **Walking speed** measured by the Timed 10-meters walk test (10-MWT), considering a clinically relevant change an improvement of 20% of the velocity (m/s) with respect to the baseline assessment.¹⁶

2.2 Secondary Aims:

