- To compare the effect of RAGT by use of the Atalante self-balance exoskeleton with conventional Rehabilitation training (cRHB), for improving **static balance**, **dynamic balance**, mobility, and **self-perception of gait impairment** measured with:
 - **Static Balance** by the Berg Balance Scale (BBS), considering a clinically relevant change for improvement in balance as measured by BBS was +3 points, meaning that PwMS are likely to perceive that as a reproducible and clinically important change in them balance performance.¹⁷
 - **Dynamic balance** by the Timed Up and Go test (TUG)¹⁸
 - **Mobility** measured by modified Rivermead Mobility Index (mRMI)¹⁹

- **Self-perception of gait** impairment by Multiple Sclerosis Walking Scale-12 (MSWS-12)²⁰
- **Instrumented gait analysis** by the G-walk device (assessing gait cycle duration, step length, propulsion index, support phase percentage D/I, oscillation phase percentage D/I, double/unique support phase percentage).
- To compare the effect of RAGT by use of the Atalante self-balance exoskeleton with conventional Rehabilitation training (cRHB) on quality of life, emotional status and fatigue measured at pre and post-intervention with:
 - Multiple Sclerosis Quality of Life-54 (MSQoL 54 Health Survey Spanish version)²¹
 - Hospital Anxiety and Depression Scale (HADs) considering a clinically relevant change of 1.7 points at HADs²²
 - The Modified fatigue scale (MFIS) ^{23 24}
 - The patient' physical effort of each session by means of the scale of perception of the effort R.P.E of Borg at the end of each training^{25 26}.
 - To evaluate the epigenetic blueprint of rehabilitation training by comparing the genome wide chromatin accessibility of peripheral blood mononuclear cells (PBMCs) before and after RAGT or cRHB, by Assay for Transposase-Accessible Chromatin sequencing (ATACseq).
 - To test the hypothesis that genome wide chromatin accessibility compared to clinical measures can be useful for identifying molecular mechanisms underlying rehabilitation therapies.
 - To compare the changes induced by RAGT versus cRHB on the overall chromatin accessibility, and specific genome regions and pathways.
 - Use the biological samples to provide additional functional and mechanistic information about the rehabilitation effects and subject health, disease or state.

3 Materials And methods

3.1 Design:

This trial is a prospective, randomized, rater-blinded study (cRHB (N=30) vs RAGT (N=30)).

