3.3 Enrollment and Screening

Subjects will be evaluated for their eligibility from neurorehabilitation and neurology outpatient clinics at the Multiple Sclerosis Center of Catalonia (Cemcat).

Potential subjects will be referred to the study via Cemcat Physicians. A member of the research team will screen the referral and confirm they meet the necessary inclusion and exclusion criteria. Following confirmation of criteria, potential subjects will be contacted by phone to schedule an initial visit for consent and baseline assessment.

Additionally, peripheral blood (6ml) will also be taken from all subjects at baseline (T1).

Prior to all testing, each of the 60 selected participants will have time to read the consent form and ask questions (see Draft Informed Consent). The consent process will take place at the Multiple Sclerosis Centre of Catalonia (Cemcat, Vall d'Hebron Barcelona Hospital Campus, [name]).

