3.4.2 Schedule

Following completion of day 1 assessments and randomization, all subjects will be scheduled for the intervention phase of the study. Each participant will receive 24 sessions of RAGT or cRHB scheduled for three times a week for 8 weeks. If a subject cancels a treatment session, it will be counted as missed session. If a subject misses three consecutive treatment sessions, they will be dropped from the study due to inconsistency in treatment carryover. Cancellations and changes in patient scheduling represent a true clinical environment and represents normal clinical patient management.

At the end of the intervention phase, a new exploration will be carried out.

[figure not shown]

Figure 1 schedule

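### The plan's only sample-size statement (15 patients, 80% power, from a 70% success rate in spinal cord injury) is not shown to be a calculation for the 30-versus-30 comparison of RAGT with cRHB

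*Combined protocol and SAP*

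**What the plan says.** Section 4 (Statistical considerations) holds the only sample-size text. On the input it says: "The sample size calculation was based on the observed success rate (70%) in a previous evaluation of safety and performance". That evaluation was of Atalante in patients with spinal cord injury, on a 10-metre walk in continuous walking mode. On the result it says: "A sample size of 15 patients had been deemed necessary to demonstrate the performance with an alpha risk of 5"%, followed by a power of 80% and a two-sided test.

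The design is described elsewhere:

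- Section 2.1, primary aim: "To compare the effect of RAGT by use of Atalante self-balance exoskeleton with conventional rehabilitation training (cRHB") on 10-MWT walking speed, "considering a clinically relevant change an improvement of 20% of the velocity (m/s) with respect to the baseline assessment". No time point is named.
- Section 3.1, design: "cRHB (N=30) vs RAGT (N=30").
- Section 3.2.1, population: MS with EDSS 6.0 to 7.0.
- Section 3.3, total: "each of the 60 selected participants will have time to read the consent form".
- Section 3.4.2, loss: "If a subject misses three consecutive treatment sessions, they will be dropped from the study". No expected rate of loss is given.

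For analysis, section 4 names the Newcombe method for comparing proportions and a matched-pairs Wilcoxon test for repeated measurements within one sample. It names no between-arm test for speed.

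**The concern.** A two-arm sample size needs a value for the comparator: a cRHB response rate, or a between-arm difference with an SD. Section 4 has neither. Its one rate comes from a different population. The plan does not say that success there meant a 20% gain in speed over the patient's own baseline. Nor does it say whether 15 is a total, a number per arm, or the size of the earlier evaluation.

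A reader will naturally take 15 patients and 80% power as the justification for this trial. If that is what is meant, the sentence does not support 60. If it is background, the plan states no basis for 30 per arm and no power or precision for its primary comparison. Either way, a null result could be read against an 80% that is not shown to have been worked out for two arms.

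**Working it through.** **1. Inputs.** From the documents: success rate 70%, two-sided 5%, 80% power, 15 patients, 30 per arm, and Newcombe for proportions. Everything else below is an assumption: cRHB or null rates, RAGT rates of 40% to 80%, losses of 10% and 20% (27 and 24 evaluable per arm), and a t-test for speed.

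**2. Can 15 be reproduced?** Not from the stated inputs, because one rate is missing. The approach is therefore to vary the missing rate and see what would give 15, with p₁ = 0.70, z = 1.960 and 0.842.

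One sample against a null p₀: n = [(1.960√(p₀(1−p₀)) + 0.842√(p₁(1−p₁))) / (p₁−p₀)]². At p₀ = 0.35: [(1.960×0.477 + 0.842×0.458)/0.35]² = (1.3205/0.35)² = 14.2, so 15.

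Two arms with control rate p₂ and mean rate p̄: n per arm = [(1.960√(2p̄(1−p̄)) + 0.842√(p₁(1−p₁)+p₂(1−p₂))) / (p₁−p₂)]². At p₂ = 0.20: [(1.960×0.7036 + 0.842×0.6083)/0.50]² = (1.8909/0.50)² = 14.3, so 15.

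| Assumed null or cRHB rate | One-sample n (total) | Two-arm n (per arm) | Power at 30 per arm, normal approximation |
|---|---|---|---|
| 20% | 6 | 15 | 98.7% |
| 30% | 11 | 24 | 89.3% |
| 35% | 15 | 31 | 79.0% |
| 40% | 21 | 42 | 65.3% |
| 50% | 47 | 93 | 34.9% |

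So 15 fits a one-sample test against about 35%, or 15 per arm against a control rate of about 20%. The plan states neither rate. The same 70% gives very different sizes depending on the missing number, and no row yields both 15 and 30.

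**3. What 30 per arm can do for responder proportions.** With Wilson limits (lᵢ, uᵢ) for each arm and d = p₁−p₂, the Newcombe interval runs from d − √((p₁−l₁)² + (u₂−p₂)²) to d + √((u₁−p₁)² + (p₂−l₂)²). Power is the sum of binomial probabilities over all outcomes whose 95% interval excludes 0. Solving for the gap that gives 80% power, at RAGT rates from 40% to 80% in steps of 1 point:

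| Evaluable per arm | True gap needed (percentage points) |
|---|---|
| 30 | 30.2–35.1 |
| 27 | 31.7–37.8 |
| 24 | 32.3–38.2 |

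Power at 30 per arm over the same RAGT rates:

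| True gap (points) | Power |
|---|---|
| 20 | 34.9–39.2% |
| 25 | 50.5–59.5% |
| 30 | 66.2–79.4% |
| 35 | 79.7–93.9% |

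For 70% versus 35%, exact power is 79.8%.

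*Precision at 30 per arm.* For observed proportions of 20% to 80%, half the total width is 19.7 to 23.8 points, so the total width is about 39 to 48 points. The interval is not symmetric. For 21/30 versus 12/30 (d = 30 points) it runs from 4.9 to 50.4, which is 25.1 below the estimate and 20.4 above it.

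**4. Continuous speed.** An unadjusted two-sample t-test (noncentral t, 2n−2 degrees of freedom) has 80% power at 0.736, 0.777 and 0.826 SD with 30, 27 and 24 per arm. The 20% change in section 2.1 is a threshold for the individual patient. It cannot be converted to SD units, because the documents give neither a baseline mean nor an SD.

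**The case against.** The strongest reply is that the calculation may have been made for two arms after all. A control rate near 20% against 70% gives 15 per arm, and the planned 30 per arm exceeds that. This stands to the extent that a two-arm origin cannot be excluded, so the point is that the link is *not shown*. It does not rescue the plan: the control rate is unstated, and 15 per arm still does not explain 30.

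A second reply is that the past tense of the sentence points to the earlier evaluation's own sample size. That is plausible, but it leaves this trial with no stated basis for its size.

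A third is that nothing here changes N or any procedure, the harm is a possible misreading, and a statement added now cannot restore a prospective justification. All of that is true, and it limits what the fix can achieve. The paragraph is nevertheless the plan's only quantitative support for randomizing 60 patients.

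A reader might go further and infer that the trial is underpowered. The documents do not support this. With an assumed 70% versus 35%, power at 30 per arm is 79.8%; with a wider gap it is higher and with a narrower one lower, and no cRHB rate is given. Nor do they support the inference that 15 is an arithmetical error, because at least two sets of unstated inputs produce it.

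**Conclusion.** The point holds in this form: the stated size and power are not shown to belong to the comparison of RAGT with cRHB in MS, and the 80% should not be quoted as its power. This conclusion rests on the text alone and needs no assumption.

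The figures on size do rest on assumptions. At 30 evaluable per arm, 80% power needs a true responder gap of about 30 to 35 points (about 32 to 38 with 27 or 24 per arm), or about 0.74 SD of speed (0.78 or 0.83). They depend on assumed RAGT rates, losses and a t-test, and on which form of the primary endpoint is analysed. They describe what 60 patients can detect. They do not show that 60 is too few, since the plan gives no expected difference to set against them.

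**What to change.** 1. Remove the sentence on 15 patients and 80% power as this trial's justification, or label it as background from the earlier evaluation and say what 15 refers to.
2. State the actual basis for 30 per arm. If it was feasibility, say so.
3. Once the primary analysis and time point are declared, replace the 80% with a dated statement, marked as not the basis on which N was chosen. Use a sourced cRHB rate or SD if the sponsor has one. Otherwise keep whichever of these matches the declared analysis:
   - *Responder proportions:* With 30 evaluable per arm, 80% power at nominal two-sided 5% (Newcombe) needs a true difference of about 30 to 35 percentage points over assumed RAGT rates of 40% to 80% (about 32 to 38 points with an assumed 27 or 24 per arm). At 30 per arm the 95% interval would have a total width of about 39 to 48 points for observed proportions of 20% to 80%.
   - *Continuous speed:* 80% power needs about 0.74 SD under an assumed unadjusted t-test (0.78 or 0.83 SD with an assumed 27 or 24 per arm). State whether the SD is that of post-treatment speed or of change.

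Give precision as a total width, because the Newcombe interval is asymmetric. Do not change N.

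The cost is one reworded paragraph, with no extra patients or procedures. The downside is that an unqualified 80% becomes a conditional and possibly less favourable figure.

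### No between-arm method is given for clinical outcomes analysed as continuous, and the Newcombe comparison is not tied to the primary endpoint, the arms or a visit

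*Combined protocol and SAP*

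**What the plan says.** Section 3.1 sets the design: "This trial is a prospective, randomized, rater-blinded study (cRHB (N=30) vs RAGT (N=30". The primary aim (section 2.1) is comparative, "To compare the effect of RAGT by use of Atalante self-balance exoskeleton with conventional rehabilitation training (cRHB) for improving" walking speed on the 10-MWT, with the benchmark "considering a clinically relevant change an improvement of 20% of the velocity (m/s) with respect to the baseline assessment". It names no visit. The secondary aims (section 2.2) repeat the comparison, "To compare the effect of RAGT by use of the Atalante self-balance exoskeleton with conventional Rehabilitation training (cRHB), for improving" balance, mobility and self-perceived gait, and again "with conventional Rehabilitation training (cRHB) on quality of life, emotional status and fatigue measured at pre and post-intervention with" the MSQoL-54, HADS, MFIS and "physical effort of each session by means of the scale of perception of the effort R.P.E of Borg".

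For these clinical outcomes, section 4 provides:

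- mean and SD for quantitative data, and frequencies for qualitative data;
- Wilson intervals for single proportions;
- "Proportions will be compared using the Newcombe formulae", with no endpoint, groups or visit attached;
- "The Wilcoxon bilateral matched-pairs test will be used to compare repeated measurement on a single sample (mean, standard deviation").

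The only explicit comparison of the two arms is the edgeR model for chromatin accessibility in section 3.4. It covers the molecular aims, which are outside this point.

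**The concern.** A matched-pairs test on one sample asks whether patients changed. The aims ask whether patients changed more on RAGT than on cRHB. Followed as written, section 4 yields no estimate, interval or test of the between-arm difference for any clinical outcome kept on its continuous scale.

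Two things are at stake. First, the primary comparison must be inferred. Responder or continuous, end of training or follow-up: the analyst could settle each after seeing the data. Second, the only p-values specified for continuous clinical outcomes are within-arm ones. Setting two such p-values side by side is not a test of the difference between arms, and its error rate is not controlled.

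**Working it through.** **1. Match each clinical outcome in the aims to a method in section 4.**

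| Outcome | Threshold in section 2 | Between-arm method available |
|---|---|---|
| 10-MWT (primary) | 20% gain in speed | Newcombe, if linked |
| BBS | +3 points | Newcombe, if linked |
| HADS | 1.7 points | Newcombe, if linked |
| TUG, mRMI, MSWS-12, G-walk, MSQoL-54, MFIS | none | none |
| Borg R.P.E. | none | none |

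Of ten outcomes, three could be served by a comparison of proportions and six cannot. Borg R.P.E. is a seventh only if it is recorded in both arms: Table 1 marks it only in the session column, whose heading refers to the robotic sessions.

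**2. Does the sample-size statement settle the primary analysis?** Section 4 gives a 70% success rate, alpha 5% two-sided, power 80% and 15 patients. It gives no comparator rate, so 15 cannot be reproduced from the plan's own inputs. Two assumed rates both return it:

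- One sample, 70% against an assumed 35%: n = [(1.96·√(0.35·0.65) + 0.842·√(0.70·0.30)) / 0.35]² = (1.321/0.35)² = 14.2, so 15.
- Two arms, 70% against an assumed 20%, pooled mean 45%: n = [(1.96·√(2·0.45·0.55) + 0.842·√(0.21 + 0.16)) / 0.50]² = (1.891/0.50)² = 14.3, so 15 per arm.

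The success-rate basis points to proportions. It does not show whether a one-sample or a between-arm analysis was meant.

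**3. Is the visit fixed?** Table 1 marks the 10-MWT at T1, T2 and one later visit (by column position T3, at 2 months). The primary aim selects none of them.

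**4. Illustration: what if within-arm tests were read as superiority?** Assumptions: 30 per arm, normal changes, the same true mean change d (in SD of change) in both arms, independent arms, and the exact two-sided Wilcoxon critical value (W ≤ 137, alpha 0.0497). Then

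P(RAGT alone significant for improvement) = P(significant improvement in RAGT) × [1 − P(significant in cRHB)].

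Within-arm probabilities are simulated, except at d = 0, where they are exact.

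| d | Product | Result |
|---|---|---|
| 0 | 0.0249 × 0.950 | 2.4% |
| 0.2 | 0.177 × 0.822 | 14.5% |
| 0.3 | 0.342 × 0.658 | 22.5% |
| 0.4 | 0.544 × 0.456 | 24.8% |
| 0.5 | 0.737 × 0.263 | 19.4% |
| 0.6 | 0.875 × 0.125 | 10.9% |
| 0.8 | 0.986 × 0.014 | 1.4% |

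With 24 per arm (an assumed 20% loss: 30 × 0.8), the figures are 20.1%, 24.7% and 23.3% at 0.3, 0.4 and 0.5 SD. In simulation under the same null, a between-arm ANCOVA falsely favours RAGT in 2.3–2.6% of trials.

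**5. Would Newcombe work if linked?** Enumerating all 31 × 31 outcomes at 30 per arm, the 95% interval falsely excludes zero in 4.5–5.2% of trials at common rates of 20–70%. So the named method would control the primary error rate adequately over that range.

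**The case against.** The strongest reply is that the primary is already covered. Section 2.1 defines a relevant gain, section 4 sizes on a success rate and compares proportions by Newcombe, and in a two-arm randomized trial the obvious proportions to compare are those of the arms. Most of this stands. A reader might infer that the trial has no between-arm method at all, and the documents do not support that: Newcombe can serve the primary, and the BBS and HADS too, and step 5 shows that it would behave well. What remains for the primary is a missing link to endpoint, arms and visit.

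A second reply is that the 25% figure measures a misuse that the plan never announces. That also stands. A reader might infer that the sponsor intends to claim superiority when only RAGT shows a significant change. Section 4 says nothing of the kind. The figure also depends on an SD of change that the documents do not give, and there is no inflation at 0 or at 0.8 SD and above.

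A third reply is that ANCOVA is a preference, since a rank test on change would also close the gap. That is correct, and the fix leaves the choice open. None of the three replies supplies a method for the six outcomes without a threshold.

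**Conclusion.** The gap is real and should be closed before analysis. It has two parts of different strength.

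- **Firm:** six secondary outcomes (seven if Borg R.P.E. is recorded in both arms) have a comparative aim and no between-arm method. This rests on the text alone.
- **Weaker, but on the primary:** the likely method is named but not attached to the 20% gain, to RAGT versus cRHB, or to a visit.

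The simulated range, from about 2% at no change through a peak of about 25% at 0.4 SD to about 1.4% at 0.8 SD, against about 2.5% for a valid test, is an illustration only. It holds under normal, equal changes and only if within-arm results were read as superiority. It is not an estimate of this trial's error rate, and it does not apply to a primary analysed by Newcombe.

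**What to change.** In section 4:

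1. **Name one primary between-arm analysis of the 10-MWT, and its visit.** T2 is suggested, for the sponsor to confirm. Either (a) the Newcombe 95% interval for RAGT minus cRHB in the proportion with at least a 20% gain in speed from T1, which fits the success-rate basis of the sample size, or (b) an ANCOVA of speed adjusted for T1 speed, reporting the adjusted difference and 95% CI. Report the other as supportive, so that there are not two candidate primaries, and tie the sample-size statement to the one chosen.
2. **Compare BBS, TUG, mRMI, MSWS-12, MSQoL-54, HADS, MFIS and G-walk between arms at T2** with a baseline-adjusted model or a rank-based version, giving the difference and 95% CI. Label these comparisons exploratory or adjust for multiplicity; G-walk alone contributes several parameters.
3. **Label the within-arm Wilcoxon tests descriptive**, and state that they will not support a claim of superiority.

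Planning anchors at 30 per arm and 80% power, not comparable with each other: about 0.74 SD (residual SD for ANCOVA) for a continuous primary; for Newcombe, a gap of 33–35 percentage points at assumed control rates of 20–50% (20 vs 54.3, 30 vs 65.1, 40 vs 74.9, 50 vs 83.3).

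Cost: SAP wording, including a re-stated sample-size basis, and a linear-model assumption to be checked by a rank-based sensitivity analysis. No new visits or patients are needed, because these outcomes are already scheduled at T1 and T2. Whether Borg R.P.E. is recorded in cRHB sessions should be clarified separately.
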